After obtaining informed consent, the research team will review standardized instructions for using the study medication with the patient and the research associate will provide a take-home kit including all of the study materials, including instructions for collecting each swab (Appendix A) and for returning the samples. Samples will be self-collected by participants at their home at intervals specified in the study instructions. All materials provided to the patient will be pre-labeled with their study ID, protecting each participant's PHI. No collections will take place in-clinic. These materials include all surveys, patient's diary, and all swab vials.

All vaginal swabs must be frozen within 48 hours of collection. As such, the participants will be asked to send their samples within 24 hours in order to give adequate time for delivery to the storage facility and be asked to collect their specimens between Sunday and Thursday so samples can reach the facility during business hours. Freezing will occur at the research site. Each patient's study kit will include a prepaid shipping envelope, which the participant can use to mail or drive their specimen to the research team who will then place it in the freezer until it is ready for analysis.

The first phase of the study will include an assessment and classification of patients' vaginal microbiome prior to receipt of the intervention. To get the best representation of the participant's baseline microbiome, the participant will be asked to collect their baseline swab no sooner than 10 days after menses, as menses-induced changes in the microbiome have been shown to resolve after this time¹². For similar reasons, if participants are being treated with an acute course of antibiotics or antifungals at the time of recruitment, they will be asked to wait 10 days after the completion of their medication course before collecting their baseline swab. There will be two additional time points for collection: collection 2) at the end of the 30 day intervention, and collection 3) 30 days after completion of the intervention.

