The intervention will take place on a rolling basis, as patient participation will have no bearing on other participants. The intervention itself will take place over thirty days. 8 pre-filled vaginal inserters with vaginal gel, will be provided to each of the participants with verbal and written instructions for application. Patients will be instructed to use Phexxi twice per week, on the same days every week. Throughout the 30 days, participants will also be asked to keep a diary of events (Appendix E) occurring when they used the product, such as intercourse or menses, as well as record any symptoms or side effects they noticed when using the product. The diary can be sent back with the second specimen vial. Disposal of the product may be done in a regular waste basket.

Approximately 30 days after completion of the intervention, participants will receive an email reminder to collect and send a third collection swab in (Appendix G) for analysis. This email will also include the link for the third and final set of surveys (B and C).

2. Data analysis and monitoring (include adverse event reporting procedures)

The pre-and post-intervention results will be compared with the subjects to serve as their own controls in this pilot study. To assess for the primary outcomes, each bacteria identified in the NextGen analyses of the composition of the pre-intervention microbiome sampling will be individually named, then classified as either “lactic acid-forming (LAF)” or “not lactic acid-forming (NLF)”. This will allow us to identify which CST each participant falls under prior to the study, and to assess if they can be classified under a different CST at the end of the study. It also allows us to conduct an independent t-test to test for significance between two variables (LAF/NLF) pre and post-intervention.

Demographic data will be collected from patient surveys. Demographic information to be collected will include age, ethnicity, number of reported vaginal yeast infections or BV infections in the last year, type of contraception used, type of diet, and medical comorbidities/current medications. This demographic information will allow us to perform a multiple regression analysis on our data set to account for confounding factors in our study population.

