- a. There is minimal risk that the privacy of the patient's medical information could be breached.
- b. There is slight risk that participants could experience side effects from the intravaginal Phexxi, as listed in the drug information in Appendix F). However, as lactic acid is a substance that typically resides in the vagina, the likelihood of serious side effects from inserting it vaginally is low.

3. Protection against risk(s):

Please see Section III, #3 above regarding protection of patient's medical information. Regarding side effects of Phexxi, the patient will be adequately counseled on the side effect profile of the treatment, and instructed to discontinue the intervention if these side effects occur and are intolerable to the patient.

If participants develop side effects, the following will take place:

- The patient will be told to discontinue the study drug, and will be withdrawn from the study. This adverse event will be reported to the RIRC.

- If the patient marked on the ICF that they would like their primary Gyn provider to be notified in the case of an adverse event, the research team will send a secure chat message (through the EMR) the patient's primary provider.
- A follow-up visit will be scheduled with the patient to ensure that the unused study drug is returned to the research team
- The patient will be responsible for seeking care from their provider, and using their insurance plan to cover the costs of any treatment required.

4. Potential benefit(s) to the subject (direct medical benefit(s)):

The direct benefit to the subject includes potential prevention and resolution of their recurrent vulvovaginitis symptoms. Additionally, the Phexxi intravaginal gel is primarily used as a contraceptive agent, and thus if the treatment is used prior to intercourse, the patient will benefit from the contraceptive effects of the treatment.

5. Alternative to participation:

Declining participation will not affect patients' medical care, as patients will not be declined the standard of care treatment for BV or yeast infections, which are antibiotics or anti-fungal agents, respectively.

Section V: Subject Identification, and Consent/Assent

1. Method of subject identification and recruitment:

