Appendix E Patient symptom diary

Subject ID

DATE	TIME		Was the product used today?	Side effects or symptoms experienced	Other events (example: menstruation, intercourse, new medications)

Please return this diary with your second collection specimen, 30 days after you have completed the study drug.

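### The diary instruction conflicts with the diary form, and the diary returns too late to trigger the in-course side-effect steps of Section IV.3

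*Protocol*

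**What the plan says.** **What to record.** Section III.1 of the protocol says: "Throughout the 30 days, participants will also be asked to keep a diary of events (Appendix E) occurring when they used the product". It also asks participants to "record any symptoms or side effects they noticed when using the product". The form itself (Appendix E) has columns for date, time, side effects or symptoms, and other events, plus one headed "Was the product used today". Nothing on the form limits the side-effects column to days of use.

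**When it comes back.** Section III.1 says "The diary can be sent back with the second specimen vial". It times the later specimens as "collection 2) at the end of the 30 day intervention, and collection 3) 30 days after completion of the intervention". Appendix E tells the participant: "Please return this diary with your second collection specimen, 30 days after you have completed the study drug".

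**What side effects should set in motion.** Section IV.3 first counsels participants to stop if side effects occur and they cannot tolerate them. It then lists what follows when side effects develop, with no reference to tolerability: the participant is told to stop, is withdrawn, and attends a visit to hand back unused drug. On reporting it says: "This adverse event will be reported to the RIRC". It names no source for the information and no time limit. The heading of Section III.2 calls for adverse event reporting procedures, but the text under it describes none.

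**What else is asked.** Survey B (Appendix C) is given before the course, immediately after it and 30 days later. It has yes/no items on symptoms in the past week and a free-text box. Survey C (Appendix D) has a free-text comment box at collections 2 and 3.

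**The concern.** There are two problems in the stated text.

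First, the protocol sentence and the form define different records. A participant who follows Section III.1 writes only about application days; one who follows the form can write about any day. The 22 diaries may then not be comparable. Reactions that arise and settle between applications would be lost for the first kind of participant. The same limit falls on menses and intercourse, which are not confined to application days.

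Second, Section IV.3 describes actions that make sense only while the gel is in use, yet the one form that asks about side effects reaches the team when the course is over. Unless a participant reports unprompted, or a document not shown tells her to, the team has no described way of learning of a side effect in time.

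At stake is the completeness of the safety record in a small single-arm pilot, and whether the promised reporting can work as written.

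**Working it through.** The protocol gives no figure for how completely side effects are captured, so there is none to reproduce. The check sets the schedule against the forms.

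**1. Days covered by the diary.** Inputs: twice-weekly use for 4 weeks and a 30-day course (Protocol, Sections I.2 and III.1). Applications: 2 × 4 = 8, which matches the 8 inserters supplied.
- Literal Section III.1 reading: 8/30 = 27% of days, leaving 30 − 8 = 22 days without an entry.
- Appendix E reading: 30/30 days can be entered.

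**2. What the literal reading would lose.** Assume application on days 0, 3, 7, 10, 14, 17, 21 and 24, and a reaction equally likely to start on any of the 30 days. It is recorded if it is present on at least one use day.

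| Duration of reaction | Share recorded |
|---|---|
| 1 day | 8/30 = 27% |
| 2 days | 15/30 = 50% |
| 3 days | 22/30 = 73% |
| 4 days | 25/30 = 83% |

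The loss falls mainly on short reactions and on those that start after the last application. The uniform onset is an assumption; burning at insertion would be recorded under either reading.

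**3. When the diary arrives.** On the same example schedule:
- With specimen 2 at day 30 (Section III.1): 30 − 24 = 6 days after the last application, and 30 days after the first.
- By the Appendix E date: about 30 days later than that, which is when collection 3 falls.

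The Appendix E sentence therefore combines the second specimen with the timing of the third. On either date dosing is over, so the diary cannot lead to a participant being told to stop or to a visit to return unused drug. No scheduled contact during the course appears in the text shown.

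**4. What Survey B adds.** It asks about itching, burning or stinging, pain, irritation, dryness, discharge and odor. With past-week recall it covers the last 7 days of the course at collection 2. At collection 3 it covers about 7 of 30 follow-up days (7/30 = 23%). It does not ask whether a symptom is attributed to the gel, and it has no urinary item. Appendix F lists UTI at 9.0% and dysuria at 3.1%. If those rates applied to 22 women (an assumption, since they come from contraceptive use), the expected counts would be 22 × 0.090 = 2.0 and 22 × 0.031 = 0.7.

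**The case against.** The strongest reply has four parts.

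- **The form governs in practice.** Participants fill in Appendix E, which has dated rows and a use question. Section III.1 says the diary is kept through the whole 30 days and gives menses as an example, which does not suit an application-day log. This is a fair reading, and it means that 27% is the coverage of one reading, not of the trial. It does not remove the conflict: participants also receive verbal and written instructions, and the sentence in the protocol still says something else.
- **Symptoms are asked about again.** A reader might infer that nothing about side effects is asked after the diary, or that only free text remains. The documents do not support that. Survey B's structured items at collections 2 and 3 overlap most of the local reactions in Appendix F. What remains missing is narrower: attribution, urinary events, and days outside the recall week.
- **A reporting instruction may exist elsewhere.** The consent and contact pages are not shown, and Section IV.3 indicates that the consent form deals with adverse-event notification. The return visit for unused drug also presupposes that the team hears early. This stands: a prompt-report instruction cannot be excluded, only noted as absent from the text shown.
- **Prompting reports has a cost.** If the broader wording of Section IV.3 applies, each reported side effect leads to withdrawal. At the Appendix F rate for burning, 22 × 0.18 = 4.0 women would leave, so 18 would remain against the target of 20. This stands as a reason to reconcile Section IV.3 first.

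**Conclusion.** The point holds in a limited form. Section III.1 and Appendix E conflict on which days are recorded (8 or 30 of 30) and on when the diary returns (end of the course, or about 30 days later). On either return date the diary comes too late to trigger the Section IV.3 steps that need dosing to be in progress. After the diary ends, no form shown asks about side effects as such, and none has a urinary item.

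A reader might go further and conclude that harm will be under-counted by a stated amount, or that infections such as those in Appendix F would be missed altogether. The documents do not support either. They give no capture rate, the 27% holds only on the literal reading, and an infection lasting several days would often overlap a use day. The Appendix F rates come from contraceptive studies and may not carry over to this schedule. Under-counting is a plausible direction of no known size.

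The conclusion rests on the text shown; a reporting contact in the consent form would weaken the point about timing but not the two conflicts. The changes are worth making before diaries are issued.

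**What to change.** 1. In Section III.1, ask for a diary entry on every day of the course, whether or not the gel was used, in line with the Appendix E layout.
2. Reconcile the return date in Appendix E with the timing of collections 2 and 3 in Section III.1.
3. Add one yes/no question on side effects, covering urinary symptoms, to the collection 3 survey set.
4. Reconcile the two triggers in Section IV.3 (side effects the participant cannot tolerate, against any side effects). This review does not say which is right.
5. After step 4, and if the consent form does not already say so, print on the diary that side effects are to be told to the study team when they occur.

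The cost is a few edited sentences in the protocol, a changed diary and one added survey item. The downside is slightly more diary burden and some extra calls to the team. Prompt reporting could also raise withdrawals if the broader Section IV.3 wording stands, which is why step 4 comes before step 5.

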The existing research on lactic acid-containing gel is promising. Of all studied methods of vaginal delivery of lactic-acid, including a douching system, a slow-release delivery pessary, lactic acid capsules, and a lactic acid-containing gel, the lactic acid-containing gel seems to be most effective. One study shows that the use of lactic acid gel as a treatment for bacterial vaginosis is comparable, but not superior to, the use of metronidazole^{8,9,10}. Currently, no research has been done on lactic acid gel as a prophylactic agent for patients who suffer from recurrent BV and/or yeast infections. This study aims to explore the feasibility and efficacy of a lactic acid-containing gel as prophylaxis against recurrent BV/yeast infections.

While several studies have been done which suggest that, as a treatment, intravaginal lactic acid gel is non-inferior to metronidazole, there have been no studies which explore its potential as a preventative agent. Compared to antibiotic therapies, lactic acid supplementation may be a more cost effective way to prevent BV and/or yeast infections, thereby reducing morbidities related to these conditions in patients who suffer from recurrent infections.

Section II: Criteria for Subject Selection

1. Number of subjects:

We will enroll a total of 22 patients. Using the Viechtbauer et al. method for calculating sample size in pilot studies¹¹, with a confidence level of 95% and probability of error prevalence estimated to at least 15%, the recommended sample size is 20. To account for exclusions and drop outs (estimated to be 10%), we should enroll a total of 22 patients.

2. Demographics of subjects:

Patients who undergo screening and are found to meet inclusion criteria will be invited to participate in this study.

Inclusion criteria

- Age 18-54
- Female
- Pre-menopausal
- Can speak and read in English
- Displays capacity for informed consent
- Has had 2 or more documented and/or self-reported episodes of symptomatic BV or candida infection in the last year, requiring, over-the-counter or prescription treatment

Exclusion criteria

- Pregnant or trying to become pregnant
- Post-menopausal
- Using NuvaRing device
- A past medical history of kidney disease, recurrent UTI, and/or urinary tract abnormalities
- Current UTI
- Using Phexxi as a contraceptive during the collection period of the study

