*Note: NuvaRing is the only medication that will be included in the exclusion criteria. While we will ask all participants to provide a list of medical conditions they have and a list of medications they are currently taking, these will be for the purposes of data analysis, and to account for possible confounders of our data.

*Note: patients do not have to be symptom-free to participate in this study. However, as stated below, if they receive antibiotic/antifungal treatment prior to starting the study, we will ask them to wait 10 days after the completion of the treatment before they collect their first swab, in order to allow for the restoration of their baseline bacterial flora.

3. Vulnerable subjects:

N/A. Pregnancy is listed as an exclusion criteria, and no minors or incarcerated persons will be included in this study.

Section III: Methods and Procedures

1. Study design and methods

This is a single center, prospective trial, which comprises of a pre-post study design will be looking at the vaginal microbiome makeup of participants before and after a four-week course of Phexxi. The primary outcomes will be an increase in lactic acid-forming lactobacilli, as well as a decrease in patient-reported symptoms of vulvovaginitis.

This study will be based at the Queen's Medical Center (QMC), [name]. Eligible patients will be approached by participating clinicians (all doctors providing care at the 1004 clinic, as delineated in the LOA form) to assess interest in study participation.. The principal investigator will review the weekly schedule for the 1004 clinic and alert the attending physicians of patients who may be eligible for the study based on chart review. A HIPAA waiver will be required for this stage of recruitment, as the principal investigator would otherwise not be accessing these patient's charts. The attending physician staffing the 1004 clinic will ask the flagged patients if they are interested in learning about the study and review general study objectives with patients. If the patient is interested in participating, the research associates will approach the patient to more thoroughly screen, then conduct the informed consent process. Informed consent will be collected from every participant prior to the start of the study.

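### The protocol makes each woman her own control but names an independent t-test for the pre-post microbiome comparison, which ignores the pairing

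*Protocol*

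**What the plan says.** Protocol Section III.1 sets out a single-arm design: "This is a single center, prospective trial, which comprises of a pre-post study design". It defines the microbiome outcome as a direction of change: "The primary outcomes will be an increase in lactic acid-forming lactobacilli". Each woman supplies a baseline swab and two later ones: "collection 2) at the end of the 30 day intervention, and collection 3) 30 days after completion of the intervention".

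Section III.2 opens on the within-woman principle: "The pre-and post-intervention results will be compared with the subjects to serve as their own controls in this pilot study". Bacteria are then classed as lactic acid-forming (LAF) or not (NLF), and the same paragraph ends: "It also allows us to conduct an independent t-test to test for significance between two variables (LAF/NLF) pre and post-intervention".

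That paragraph also plans a separate look at community state type (CST), "to assess if they can be classified under a different CST at the end of the study". The next paragraph plans a multiple regression to account for confounders. No paired t-test, signed-rank test, change-score analysis or mixed model is named anywhere in the protocol.

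**The concern.** An independent t-test assumes that the two sets of values come from unrelated subjects. Here there is no second group, and one paragraph commits to both a within-woman comparison and a between-group test.

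The named sentence can be read in two ways, and independence fails in both:

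- **Pre against post.** The two values come from the same woman.
- **LAF against NLF.** The two values come from the same swab. This comparison also does not measure the stated outcome, which is a rise in LAF organisms within a woman.

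An independent test of change scores is not available either, because it needs a comparison group. The confounder regression does not deal with the pairing.

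Using women as their own controls is meant to remove the variation between women, and the named test puts it back. With about 20 women, a real shift could be missed, and the confidence interval carried into any later trial would have the wrong width. The statistical analysis plan was not available, but this is not a detail left open for it: the protocol itself fixes the test.

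**Working it through.** **Sample size, to see whether it depends on this test.** Section II.1 uses a pilot-study formula with 95% confidence and a 15% problem probability: n = ln(1 - 0.95) / ln(1 - 0.15) = 18.43, rounded up to 19. The protocol states "the recommended sample size is 20", close to this. Adding 10% gives 20 × 1.10 = 22 enrolled. Neither figure uses a t-test, so changing the test leaves both as they are.

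**Standard error of the mean change.** Take n pairs, the same SD at both times, and pre-post correlation ρ.

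- Independent test: SE = SD × √(2/n)
- True (paired): SE = SD × √(2(1 - ρ)/n)
- Ratio, independent to true: 1/√(1 - ρ), which equals 1 only at ρ = 0

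With n = 20 and SD = 1, the independent SE is √(2/20) = 0.316 at every ρ. The true SE at ρ = 0.5 is √(2 × 0.5/20) = 0.224, a ratio of 1.41.

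**Error rates and power.** The inputs are 20 pairs (Section II.1), a two-sided 5% level, normal data and equal SDs. Apart from the 20, these are assumptions, as are ρ and the shift of 0.66 SD, because the protocol gives none of them for this test. The shift is illustrative: it is the one that a paired test detects with 80% power at ρ = 0.5. Results are from 400,000 simulated trials per correlation, comparing a two-sample t (38 df) with a paired t (19 df).

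| ρ | SE ratio | Type I error, independent | Power, independent | Power, paired |
|---|---|---|---|---|
| -0.2 | 0.91 | 7.3% | 53% | 44% |
| 0 | 1.00 | 5.0% | 53% | 51% |
| 0.1 | 1.05 | 3.9% | 53% | 55% |
| 0.2 | 1.12 | 3.0% | 53% | 60% |
| 0.3 | 1.20 | 2.1% | 53% | 66% |
| 0.5 | 1.41 | 0.7% | 54% | 80% |
| 0.7 | 1.83 | 0.1% | 55% | 95% |

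The paired test holds 5.0% type I error throughout. The mean confidence interval from the independent test is 1.16, 1.38 and 1.77 times as wide as the paired one at ρ = 0.3, 0.5 and 0.7.

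The shift needed for 80% power, independent against paired, is:

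- ρ = 0: 0.91 against 0.93 SD
- ρ = 0.3: 0.87 against 0.78 SD
- ρ = 0.5: 0.84 against 0.66 SD
- ρ = 0.7: 0.80 against 0.51 SD

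**A different shift.** At 0.5 SD, power is 31% against 43% at ρ = 0.3, 29% against 57% at 0.5, and 25% against 78% at 0.7. The direction is the same, but the percentages depend on the shift chosen.

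**The LAF-against-NLF reading.** If the two are complementary shares of one swab, their correlation is -1 and the SE ratio is 1/√(1 + 1) = 0.71. The independent test then rejects a true null about 17% of the time at a nominal 5%.

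**The case against.** The strongest reply is that this is a pilot. Its size comes from a pilot-study formula, so no power target is broken. Both tests use the same mean difference, so the estimated shift does not change; only its standard error, interval and p-value do. Under positive correlation the test is conservative, and at a correlation of 0.1 the power gap is two percentage points. The own-controls sentence also suggests that the word independent may be a slip.

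All of that is true, and it limits the harm. It does not make the text right. The protocol says that it will test for significance, and a small sample can least afford to lose precision. If the word is a slip, correcting it is all the more straightforward.

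Three further cautions stand. The 0.66 SD shift is an assumption, and the power figures move with it. Normality is doubtful if LAF is analysed as a share of the sample. The main table covers only the pre-against-post reading; on the LAF-against-NLF reading the error runs the other way, towards false positives.

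It is also fair that the protocol says only post-intervention while there are two later swabs, so the choice of time point belongs to the investigators. The end-of-intervention swab fits the design statement best: "a pre-post study design will be looking at the vaginal microbiome makeup of participants before and after a four-week course of Phexxi".

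**Conclusion.** The concern holds. The protocol fixes a test for unrelated groups for a within-woman comparison on a primary outcome, and contradicts its own design statement in the same paragraph. That the test is wrong for paired data unless the correlation is zero follows from the algebra and needs no assumed figure.

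The size of the effect does need assumptions. For correlations of 0.3 to 0.7 and a 0.66 SD shift with 20 pairs, the named test gives up about 13 to 40 points of power (66 - 53 and 95 - 55). At zero correlation nothing material is lost, and at negative correlation the test is anti-conservative. The sample size of 20 evaluable and 22 enrolled, and the CST assessment, are unaffected. The wording must be corrected before the analysis.

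**What to change.** In Section III.2, replace the independent t-test with a paired test of each woman's change in the LAF measure from baseline to one stated later swab, reported with a 95% confidence interval. Collection 2 is the natural choice of later swab. Choose the paired t-test or the Wilcoxon signed-rank test in advance. A mixed model with a random intercept per woman over the three collections is an acceptable alternative.

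Do not test LAF against NLF as a measure of change. If the two are expressed as shares of the sample, report NLF only as the complement of LAF.

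The cost is one sentence of protocol wording, changed before analysis, with no extra participants, swabs or assays.
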